**Statistics**

-Subgroups will be defined by cancer type, cancer invasiveness, skin type, and gender

- The sample size is likely to be 20-100 participants as estimated by the established patients at the office of [name] MD and the frequency of carcinoma diagnosis.
- On a per-case basis, treatment is considered effective if there is no clinical/histological recurrence in 5 years.
- For the study as a whole, the treatment is considered effective if the recurrence rate is lower or approximately equal to the comparison groups: other FDA approved/traditional treatment options. For example, studies have shown that after surgical excision, over 5 years, superficial BCC recurrence rate is between 2% and 5%, nodular BCC 2-8%, SCC in situ ~0.8%, and invasive SCC between 1.7% and 6.4%. And, most surgical excision recurrences occur within 2 years. Other methods such as electrodessication and curettage have higher recurrence rates. So, we would consider our treatment successful if our recurrence rates are lower or approximately equal to any of the approved treatment options.
- Treatment is not randomized. Participation is determined by the patient's willingness to participate. If they participate they are given the treatment. No placebos or control groups.

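### The study-level success rule judges the observed recurrence rate with no allowance for sampling error, so at the low end of 20-100 participants, for low benchmarks and within histology groups, a success verdict is weak evidence

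*Protocol*

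**What the plan says.** All of this is in the protocol's Statistics section.

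- The study-level verdict: "For the study as a whole, the treatment is considered effective if the recurrence rate is lower or approximately equal to the comparison groups". The comparison groups are external, since the section also says there are no controls.
- The verdict is restated more loosely a few lines later: "we would consider our treatment successful if our recurrence rates are lower or approximately equal to any of the approved treatment options".
- The size: "The sample size is likely to be 20-100 participants as estimated by the established patients" and by how often carcinoma is diagnosed there. No error rate, power or precision is attached to it.
- Five-year recurrence after surgical excision, given as examples: "superficial BCC recurrence rate is between 2% and 5" per cent; "nodular BCC 2-8" per cent; "SCC in situ ~0.8%, and invasive SCC between 1.7% and 6.4" per cent.
- Electrodesiccation and curettage is said to have higher recurrence, with no figure.
- A single case counts as a success if it has no clinical or histological recurrence in five years. Subgroups include cancer type and invasiveness, which is how the benchmarks are printed.

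**The concern.** The protocol sets a rule for its main conclusion, and that rule compares an observed proportion with a published one. With 20 to 100 participants one recurrence moves the observed rate by 5 points (1/20) to 1 point (1/100), while the printed benchmarks run from 0.8% to 8%. A low observed rate can therefore arise by chance from a treatment whose true rate is well above the benchmark, and nothing in the rule guards against this.

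The verdict rests on this rule alone, because the study has one arm. The Study Objective is to reduce the need for surgery, and publication is planned. The background section already reports complete clearance over one year in the practice's earlier subjects. A perfect or near-perfect record in a small series is the result that such a rule would over-read.

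**Working it through.** **Inputs.** Sizes 20, 50 and 100: the two ends of the stated range and one value between. Benchmarks b = 0.8%, 2%, 5%, 6.4% and 8% from the Statistics section. Assumptions: one lesion per participant, independent outcomes, complete five-year follow-up. The plan gives no derivation of its sample size, so there is no figure to reproduce.

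**Step 1: how often a doubled rate passes.** Read strictly, the rule passes when the number of recurrences X is at most c, where c is n × b rounded down. With true rate 2b, the probability of passing is P(X ≤ c), with X binomial(n, 2b).

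| Benchmark (true rate) | n=20 | n=50 | n=100 |
|---|---|---|---|
| 0.8% (1.6%) | c=0: 72% | c=0: 45% | c=0: 20% |
| 2% (4%) | c=0: 44% | c=1: 40% | c=2: 23% |
| 5% (10%) | c=1: 39% | c=2: 11% | c=5: 6% |
| 6.4% (12.8%) | c=1: 25% | c=3: 10% | c=6: 2% |
| 8% (16%) | c=1: 15% | c=4: 8% | c=8: 1.5% |

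Example: 0.984^20 = 0.724 for the first cell.

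**Step 2: histology groups.** The benchmarks are specific to histology, so the denominators may be smaller. If 100 participants split evenly over the four listed histologies (an assumption; the protocol gives no split), each group has 25. A doubled rate then passes 67%, 36%, 27%, 15% and 21% of the time, in the table's order.

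**Step 3: the effect of the loose wording.** If near-equality is read as two points above the benchmark (an assumption), a true 10% against 5% at n=100 passes when X ≤ 7. That is 21% of the time, compared with 6% on the strict reading. The choice of comparator matters as much: the same true 10% judged against 8% (X ≤ 8) passes 32% of the time at n=100. Curettage, with a higher rate but no figure, would be more lenient still.

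**Step 4: what the best possible result can show.** With zero recurrences the exact one-sided 95% upper limit is 1 − 0.05^(1/n):

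- n=20: 13.9%
- n=50: 5.8%
- n=100: 2.95%

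At n=20 even a perfect result excludes none of the printed benchmarks. The number of event-free lesions needed to put this limit below b is ln(0.05)/ln(1 − b), rounded up: 36 for 8%, 46 for 6.4%, 59 for 5%, 149 for 2% and 373 for 0.8%. With no margin, the last two exceed 100.

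**Step 5: SCC in situ.** One recurrence in 100 is 1.0%, already above 0.8%, so on a strict reading only zero recurrences pass. A treatment whose true rate is 0.8% has zero recurrences in 100 with probability 0.992^100 = 0.448, so it fails 55% of the time.

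**The case against.** Four points can be made on the other side.

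1. **A reader might infer that a clearly worse treatment is often declared successful across the whole stated range.** The documents do not support that. With all 100 participants against one benchmark of 5-8%, a doubled rate passes only about 1.5-6% of the time. At a limit of 8%, a true 10% passes 39%, 43% and 32% of the time at n=20, 50 and 100. But two points above the limit is arguably what the protocol means by near-equality, so those figures do not show that a clearly worse treatment passes. This objection stands and limits the point to small samples, low benchmarks and histology groups.

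2. **A reader might infer that the SCC in situ benchmark can never be met.** That treats an approximate 0.8% as a hard cut-off. Under the protocol's wording, 1 in 100 could be called approximately equal, and a margin could make a claim reachable. The 373 applies only with no margin and an exact 95% limit. This stands too; but the protocol states no margin.

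3. **The verdict is for the study as a whole, and the excision rates are examples.** True, so the 25-per-group figures are illustrative. Yet the only rates offered are by histology, and no pooled benchmark is given.

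4. **Interval methods usually belong in a statistical analysis plan, which is not at hand.** The choice of interval does. The success rule, however, is stated here, and adding a confidence limit later would change it. Whether patients would be told that the treatment equals surgery is conjecture: the documents state only an intention to publish.

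**Conclusion.** The concern holds in a limited form. The protocol lets an observed rate decide success, with no sampling allowance, no defined margin and a free choice of comparator. On a strict reading, a doubled rate passes 39% of the time at n=20 against 5%, 20-72% across the planned sizes against 0.8%, and 23-44% against 2%. The risk falls to about 1.5-6% only if all 100 participants are compared with a single 5-8% benchmark and the strict reading is kept. A perfect result in 20 participants leaves rates up to 13.9% open.

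The figures rest on one lesion per participant and full five-year follow-up. Losses, which the protocol lists as a potential bias, would reduce the numbers assessed and weaken the evidence further.

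**What to change.** In the Statistics section:

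1. Replace the choice of any approved option with one comparator rate per histology, fixed in advance, and state a numerical margin for approximate equality. Both values are for the investigator to justify.
2. Claim success in a comparison only if the exact one-sided 95% upper limit of the recurrence rate lies below comparator plus margin. Otherwise report the rate with its exact 95% interval and no success verdict.
3. State beside the 20-100 what that size can support. For example, if comparator plus margin were 8%: no claim is possible below 36 assessed lesions; zero recurrences are needed at 50 (limit 5.8%; one recurrence gives 9.1%); at most 3 are allowed at 100 (limit 7.6%; four give 8.9%).
4. Report SCC in situ descriptively, with no equality claim against 0.8%.

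**Cost.** Protocol wording and one exact interval per comparison; no extra patients. The real price is that success is harder to claim at every planned size. Against a limit of 8%, a true 5% rate passes 0.95^50 = 8% of the time at n=50, and P(X ≤ 3) = 26% at n=100. A true 8% passes 1.5% and 3.7% of the time. The margin is therefore essential: without it the rule would demand superiority and drop the protocol's near-equality branch. Small samples will give an estimate only.

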**Patient retention:** Patients will be instructed of the importance of returning to the office for the scheduled follow ups. Patients will be closely tracked and monitored. We collect cell, home, mobile, and emergency numbers, emails, and addresses from all patients under our care. This provides multiple ways to contact patients. Patients will be instructed to make follow up appointments before leaving the office, if they don't then we will call when they are due. Patients are always called, texted, and/or emailed prior to their appointments to confirm. No show patients will be contacted multiple times. If no response is given after multiple electronic attempts, then letters are mailed to patients. These letters outline the importance of returning to the office for care and the risks associated with not returning.

**Patient criteria:** Participants must have a biopsy confirmed (by a pathologist or dermatopathologist) BCC and/or SCC and/or an hypertrophic actinic keratosis (solar keratosis) that extends to the base of a specimen and a BCC or SCC cannot be ruled out by the dermatopathologist. The carcinoma can be any level of invasiveness. Patients can be of any skin type, demographic, ethnicity or gender. The carcinoma cannot have been previously treated by any other means (surgical excision, laser, Mohs, electrodisssection, topical, etc.) Patients must be 18 years or older. Patients cannot be pregnant. We do not declare any other exclusion criteria in relation to previous or current diagnoses, surgeries, or medications.

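### The study-level success rule has an ambiguous comparator, no pooled benchmark and no limit for approximate equality, so intermediate results can be called success or failure after the fact

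*Protocol*

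**What the plan says.** All of this is in the protocol; no SAP is shown.

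- **The rule, stated twice in one Statistics bullet.** For the study as a whole, "the treatment is considered effective if the recurrence rate is lower or approximately equal to the comparison groups", which the sentence goes on to describe as other FDA-approved or traditional treatments. The bullet ends: "we would consider our treatment successful if our recurrence rates are lower or approximately equal to any of the approved treatment options".
- **The benchmarks.** Five-year figures are offered as an example and for surgical excision only: "superficial BCC recurrence rate is between 2% and 5%, nodular BCC 2-8%, SCC in situ ~0.8%, and invasive SCC between 1.7% and 6.4" per cent. Of the alternatives it says: "Other methods such as electrodessication and curettage have higher recurrence rates". No figure follows.
- **Level of analysis.** The primary outcome, under Outcomes of interest, concerns all participants. Cancer type and stage are secondary outcomes, and in Statistics they are subgroups: "Subgroups will be defined by cancer type, cancer invasiveness, skin type, and gender".
- **Who is enrolled.** Under Patient criteria, "The carcinoma can be any level of invasiveness". The same paragraph also admits "an hypertrophic actinic keratosis (solar keratosis) that extends to the base of a specimen" where carcinoma cannot be excluded. The Patient population paragraph requires confirmed BCC and/or SCC.
- **Size.** "The sample size is likely to be 20-100 participants", based on patient availability. There is no control group.

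**The concern.** With no control group, this rule is the only basis for calling the treatment comparable to established options, and publication is planned. It leaves three things open.

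1. **Comparator.** If *any* means at least one option, the weakest sets the bar, and the option described as weaker than excision has no stated rate. If it means every option, the bar is far stricter.
2. **Benchmark.** A pooled verdict needs a pooled benchmark, and none is given. The type-specific figures span a factor of ten. Hypertrophic actinic keratoses have no figure.
3. **Limit.** Nothing says how far above a benchmark still counts as approximately equal, or whether the point estimate or an interval is judged.

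The treating team collects outcomes openly, so these choices could be made with the results in view.

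**Working it through.** **Inputs (Statistics).** Excision benchmarks: superficial BCC 2–5%, nodular BCC 2–8%, SCC in situ about 0.8%, invasive SCC 1.7–6.4%. Size 20–100. That size is a feasibility range, so there is no calculation to reproduce.

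**Step 1: one result against each listed figure.** Pooled 4/100 = 4.0% (exact 95% interval 1.1% to 9.9%). It is below 5%, 6.4% and 8%, and above 0.8%, 1.7% and 2%. No assumption about tumour mix is needed.

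**Step 2: how much the choice of bar matters.** Assume a true pooled rate of 5% and n = 100. The chance that the point estimate is at or below bar *b* is P(X ≤ k), where X is Binomial(100, 0.05) and k is the largest whole number not above 100*b*.

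| Bar | k | Chance of passing |
|---|---|---|
| 0.8% | 0 | 0.6% |
| 1.7% | 1 | 3.7% |
| 2% | 2 | 11.8% |
| 5% | 5 | 61.6% |
| 6.4% | 6 | 76.6% |
| 8% | 8 | 93.7% |

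**Step 3: a pooled benchmark depends on the mix and on the end of the range.** Both mixes below are assumptions, per 100 lesions.

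- Even mix, 25 of each type. Upper ends: 25 × (0.05 + 0.08 + 0.008 + 0.064) = 5.05. Lower ends: 25 × (0.02 + 0.02 + 0.008 + 0.017) = 1.625.
- In-situ-heavy mix, 70 SCC in situ and 10 of each other type. Upper ends: 70 × 0.008 + 10 × (0.05 + 0.08 + 0.064) = 2.50. Lower ends: 70 × 0.008 + 10 × (0.02 + 0.02 + 0.017) = 1.13.

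So 4/100 lies between the two ends for the even mix and above both for the in-situ-heavy mix.

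**Step 4: point estimate or interval.** With no recurrences, the exact two-sided 95% upper limit is 1 − 0.025^(1/n). For n = 20 it is 16.8%; for n = 100 it is 3.6%. Thus 0/20 passes every point-estimate reading, while its upper limit exceeds every listed benchmark.

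**Step 5: what an interval rule would demand.** The smallest number of lesions, all free of recurrence, with an upper limit below benchmark plus margin is ln(0.025) / ln(1 − benchmark − margin), rounded up. Upper-end benchmarks are used, and the margins are illustrations.

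| Margin | Even mix (5.05%) | In-situ-heavy mix (2.50%) |
|---|---|---|
| 2 points | 51 | 81 |
| 5 points | 35 | 48 |
| 10 points | 23 | 28 |

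**The case against.** The strongest reply has four parts.

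- **The comparator does not change.** A reader might infer that the two sentences name two different comparators. They do not: read in full, the first also refers to approved or traditional treatments, nearly the same class. What stands is the ambiguity of *any*, and the lenient reading is not the only one.
- **The level is not wholly open.** A reader might infer that pooled and by-type verdicts are equally supported. The primary outcome, the reference to the study as a whole, and the placing of type and stage under secondary outcomes and subgroups all favour pooling. What stands is that no pooled benchmark exists and nothing says how a mixed result bears on the verdict.
- **Detail belongs in the SAP.** An interval rule or a choice of range end is often left there, and the excision figures are introduced as an example. That is fair for missing detail. But the protocol itself states the verdict rule, and a success claim against an unquantified option, or on 0/20, would comply with a permissible reading of it.
- **Not every result is affected.** Zero recurrences pass under every point-estimate reading. The conflict over which listed figure applies concerns intermediate results. This stands and limits the point.

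**Conclusion.** The point holds in this limited form. The Statistics section fixes the study-level verdict badly: *any* is ambiguous, the pooled verdict that the structure favours has no benchmark, and approximate equality has no limit. Intermediate results such as 4/100 can be called success or failure once seen. At a true rate of 5% and n = 100, the choice among listed figures moves the chance of passing from 0.6% to 93.7%. That range assumes a point-estimate rule, one lesion per participant and complete follow-up.

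A reader might go further and infer that the rule would usually pass a clearly inferior treatment. The documents do not support this. It would need an assumed tumour mix and a single bar, such as 8% for all lesions, that the protocol nowhere states. The effect of taking electrodesiccation and curettage as the bar cannot be quantified, because no rate is given.

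**What to change.** Rewrite the success bullet in Statistics.

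- **(a) Comparator.** Replace the reference to any approved option with surgical excision, the only option with listed rates. Alternatively, give every other option a stated rate by tumour type and say that each must be met.
- **(b) Level and benchmark.** State that the verdict is pooled, against the 5-year rate expected from the listed excision figures for the enrolled tumour mix, using the same pre-chosen end of every range. Report types descriptively with exact intervals. Report hypertrophic actinic keratoses separately, since they have no benchmark, and reconcile their eligibility between Patient population and Patient criteria.
- **(c) Limit.** Replace approximate equality with a numerical margin chosen by the sponsor and written into the protocol now, before further outcomes are collected. Claim a lower or comparable rate only if the upper limit of the two-sided 95% interval lies below benchmark plus margin; otherwise report descriptively. Use one index lesion per participant for the exact interval, or an interval that allows for clustering. Use a 5-year estimate that accounts for withdrawn participants and does not count them as cured.
- **(d) Size.** State beside the 20–100 range that 0/20 leaves an upper limit of 16.8% and 0/100 leaves 3.6%.

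**Cost.** Wording and a little analysis, with no added visits. The price is that many results will be descriptive only. With the illustrative margins, which are not recommendations, no claim is possible at n = 20 under either assumed mix. A 2-point margin needs at least 51 lesions (even mix) or 81 (in-situ-heavy mix) without a single recurrence. Losses to follow-up make a claim harder still.

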#### **Ethics, Privacy, and Pharmacovigilance Reporting**

- ethical consideration is important for this study. We use human participants. If not monitored closely, the skin cancers have a risk to progress and cause damage to the patient's skin at the affected area. Survival rate for BCCs and SCCs is almost 100% therefore there is a very low risk of death. We will be submitting our study for ethics approval prior to starting.
- We will protect patient personal data and confidentiality in accordance with HIPAA guidelines. Our office already follows HIPAA and all employees are well informed of the policy. No PHI as outlined by HIPAA will be reported or shared from our study in any publications or shared with any individual not responsible for the direct care of the patient. Letters and/or numbers will replace names when referring to subjects when reporting or referring to data. Photos or videos taken of participants will not include identifying characteristics unless rights were signed off by the patient. Informed consent will be obtained prior to any individual's participation in our study. A detailed consent form will be reviewed with the patient and the patient will be required to sign before being treated. If the patient has caretakers or family members that are responsible for assistance with their care they will also be present in the review of consent.
- Patients will be instructed of the importance of returning to the office for the scheduled follow ups. Patients will be closely tracked and monitored. We collect cell, home, mobile, and emergency numbers, emails, and addresses from all patients under our care. This provides multiple ways to contact patients. Patients will be instructed to make follow up appointments before leaving the office, if they don't then we will call when they are due. Patients are always called, texted, and/or emailed prior to their appointments to confirm. No show patients will be contacted multiple times. If no response is given after multiple electronic attempts, then letters are mailed to patients. These letters outline the importance of returning to the office for care and the risks associated with not returning. If after all attempts to contact the patient are unsuccessful, they will be labeled as withdrawn from the study. This will be noted in our data. If the study is terminated, all participants will be closely monitored as outlined in the study protocol. If the site is terminated, participants will be instructed to find another dermatologist to track the recurrence of their

skin cancer. Medical records and research data will be sent to their new dermatologist once a patient signs a medical record release. Care will then be transferred over to their new dermatologist.

-For adverse reactions/adverse events: All adverse reactions will be noted and reported in our study. A new plan of care will be designed for the patient ensuring the proper treatment of their skin cancer.

-We plan to publish this study in a scientific journal.
